1.7.2 Known Potential Benefits

The purpose of this study is not to investigate a possible benefit for each subject. We do not know whether these video images truly identify cancerous tissue, so we cannot guarantee any benefits from being part of this study. However, there is a chance that because of the video images, the surgeon will remove additional cancerous tissue that they would not have removed during a standard operation.

1.7.3 Assessment of Potential Risks and Benefits

The PI weighs the risks of participating in the study with the potential benefits of participating in the study for each subject enrolled. We feel that the very low risk of adverse reactions expected from the study compared to the practical potential benefit of improving nervous system tumor resection and related outcomes using a non-toxic imaging agent are acceptable.

2 Study Objectives

The primary study objective is to determine safety/efficacy of high dose, delayed indocyanine green (second window ICG) during surgery of nervous system tumors.

The first objective is to determine diagnostic test characteristics (sensitivity/specificity) of delayed, high dose indocyanine green (second window ICG) as a diagnostic aid during surgery of nervous system tumors. Additionally, to optimize timing and dose of second window IcG during surgery of nervous system tumors, based on sensitivity/specificity. Lastly, to compare SOC dyes with indocyanine green to determine efficacy for tumor visualization, answering the question is one dye superior to another, more accurate and precise.

3 Study Design

3.1 General Design

This study is a single center, open-label, two-part study to assess image guided surgery of intramolecular imaging in nervous system tumors. Subjects with a diagnosis of a resectable nervous system tumor who are at risk of recurrence are included. The primary goal is to observe what tissues fluoresce in the OR, and then to identify if that tissue is cancerous/tumor or normal when the histopathology is performed.

This study is split into two parts. The purpose of Part 1 is to confirm dose, assess timing of the operation and assess the feasibility of using indocyanine green as a fluorescent for neurosurgical tumor resection without extending surgery beyond what is seen on the standard of care MRI. The purpose of Part 2 is expansion of the margin view phase of the operation, where residual fluorescence can be resected at the discretion of the surgeon; in addition, further evaluation of optimal dosing and timing.

CONFIDENTIAL

Candidates are those with a presumed tumor in the nervous system that requires surgery. There is no randomization or control group.

Subjects undergo indocyanine green injection within 72 hours prior to surgery. Permitting infusion time within 72 hours of operation is believed to be adequate for tissue glow/surgical visualization. Alternately, patients may receive 25 mg of indocyanine green during induction. Dose and time of administration will be determined by the neurosurgeon during surgical planning. This 25 mg dose of indocyanine green is similar to dosing for other intraoperative vascular visualization.

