The standard of care dye, Gleolan™, is the first *and only* FDA approved optical imaging agent for use in Fluorescence-Guided Surgery. Gleolan [aminolevulinic acid hydrochloride (ALA HCl)] is an optical imaging agent indicated in patients with glioma (suspected World Health Organization Grades III or IV on preoperative imaging) as an adjunct for the visualization of malignant tissue during surgery. It is orally administered 2-4 hours prior to anesthesia. A standard surgical operating microscope adapted with a blue light emitting light source and ancillary excitation and emission filters to visualize fluorescence excitation in the wavelength of 375 to 440 nm and for observation from 620 to 710 nm will be used to view Gleolan (50, 51, 52).

In this current study, we intend to compare SOC dyes with indocyanine green to find out which dye is more accurate and precise. This may lead to patients receiving more than one (1) drug prior to surgery and visualizing the tumor with different cameras during surgery.

There are no additional risks of administering both dyes. However, due to imaging with multiple cameras, the surgical procedure may be prolonged 15 minutes. In this study, there is no anticipated risk by extending the surgical procedure.

As of January 2019, this protocol completed Part 1, observational, and began Part 2, permitting deviation from the surgical plan based on indocyanine green intraoperative imaging, of the study. A total of 327 subjects consented with 296

CONFIDENTIAL

This material is the property of the University of Pennsylvania.

subjects receiving infusion of indocyanine green and 26 non-evaluable subjects (4 subjects have been consented but not infused as of yet). The reasons for non-evaluable subjects are the following: iodine/shellfish allergy (4 subjects), surgical procedures cancelled (4 subjects), decline participation (9 subjects), scheduling conflicts (5 subjects), and clinical issues (4 subjects; i.e., pre-infusion hypertension [HTN]; no medical clearance for surgery).

Of the 296 subjects infused, 110 subjects were administered 2.5 mg/kg and 186 subjects were administered 5 mg/kg of indocyanine green. Of 296 infusions, there were 55 total adverse events (AEs) observed in 35 patients, which are presented in more detail in [Section 1.7](#) below.

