1.7 Risk/Benefit Assessment

1.7.1 Known Potential Risks

Risks of Indocyanine Green:

The risks of using indocyanine green are well described and exceedingly rare [15, 28]. Indocyanine green is known to have a rare but serious side effect known as anaphylaxis and because of this, patients with a history of iodide allergies will not be considered candidates in this study. There is no connection with any other particular contrast agent or drug or food allergy. Anaphylaxis is an allergic reaction to a substance that can cause swelling of the skin, shortness of breath, dizziness, increased heart rate (HR), rash, and/or death. The indocyanine green dye will be administered in a procedure room with trained nurses who will closely monitor the subject's vital signs (HR, blood pressure [BP], oxygen level [pulse oximetry], and skin color) to check for any signs of anaphylaxis. In the event of an anaphylactic reaction, the indocyanine green injection will be stopped and medication will be used to control the reaction. One study placed the rate of adverse reactions for indocyanine green injections at fewer than 4 in 240,000 [29].

Adverse Events (as of January 2019):

The AEs table below outlines the number of events that occurred by Common Terminology Criteria for Adverse Events (CTCAE) v4.0 event category in this protocol as of January 2019. Subjects could have had more than one AE. Of 296 infusions, there were 55 total AEs observed in 35 patients: 36 events in the 5 mg/kg dose cohort and 19 events in the 2.5 mg/kg dose cohort. Out of the 55 AEs, one was a serious adverse event (SAE) (HTN). One patient experienced two unique AEs during infusion (HTN-General Disorder).

Overall, in 296 patients, HTN accounted for 5.7% of AEs; mild arm pain/discomfort accounted for 7.4% of AEs, general disorders accounted for 2.7%, administration site conditions accounted for 2% of AEs and 0.6% patients reported a gastrointestinal issue.

Of the patients in the **5 mg/kg dose cohort**, 5.4% reported vascular disorders, 9.1% reported mild arm discomfort or pain, 3.2% had general disorders and 1.6% had administration site conditions.

Of the patients in the **2.5 mg/kg dose cohort**, 6.4% reported vascular AEs, 4.6% of them had mild arm discomfort or pain, 1.8% had general disorders, 2.7% had administration site conditions and 1.8% had gastrointestinal AEs.

CONFIDENTIAL

This material is the property of the University of Pennsylvania.

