5.1.2 Treatment Regimen

The dose is a single infusion of up to 5 mg/kg reconstituted indocyanine green injected intravenously in the dark, within 72 hours of the operation. Alternately, subjects may receive a 25 mg dose of indocyanine green administered by the anesthesiology team during induction. If subjects experience any AEs, please reference [Section 8.2](#) for protocol intervention. There is no second dose.

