Margin View: After completion of the surgery based on standard techniques, the NIR imaging system (i.e. VS₃ Iridium, Stryker 1588 AIM) will be used to determine if there is any residual fluorescence in the resection bed. In Part 1 of this study, the surgeon will proceed to biopsy suspected areas of residual or abnormal tissue or abnormal fluorescence without extending surgery beyond what is seen on the standard of care MRI. In Part 2 of this study, the surgeon will proceed to resect suspected areas of residual or abnormal tissue or abnormal fluorescence. These biopsy and/or resected sites will be correlated with the final pathology, which will be considered the gold standard. Fluorescence of the biopsy and/or resected specimen with the NIR imaging system will be studied both *in vivo* and *ex vivo*. In addition, surgeon's judgment as to whether the biopsy and/or additional resection specimen represents tumor will be recorded in a binary outcome questionnaire (yes/no).

Final View: Last, prior to closing a final view of the cavity will be obtained with the NIR imaging system – Final View.

Ex Vivo View: Specimens will be placed in a specimen cup. These specimens will be imaged on a back table with the NIR imaging system.

Once the tumor is resected, a small section of the path specimen will be divided and appropriately labelled: 1) histopathology, 2) research lab specimen. Each tissue sample will be placed in its own unique specimen cup. The tissue will be sent to pathology for standard processing, following OSHA and Institutional policy and procedures for tissue handling and transport.

Of note, it is not always possible to be sure of diagnosis prior to surgical sampling and pathologic analysis. Nevertheless, all subjects and specimens will contribute to the final analysis. For example, if the subject is thought to harbor a malignant

CONFIDENTIAL

This material is the property of the University of Pennsylvania.

glioma, but at the time of surgery, an intraoperative diagnosis of lymphoma is made, this subject's pathology and indocyanine green fluorescence status will still contribute to the final analysis plan.

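### Part 1 holds no 25 mg induction subjects, and section 7.1 would pool that regimen's Part 2 specimens into an endpoint that section 3.2 defines for second-window ICG

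*Combined protocol and SAP*

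**What the plan says.** On the role of the parts, section 3.1 states: "The purpose of Part 1 is to confirm dose, assess timing of the operation and assess the feasibility of using indocyanine green". The same sentence keeps surgery within what the standard MRI shows. Section 3.1 then gives Part 2 two purposes: discretionary resection of residual fluorescence, and continued work on dose and timing. The operating rule is in section 6.3. In Part 1, suspicious margin areas are biopsied. For Part 2 it says: "In Part 2 of this study, the surgeon will proceed to resect suspected areas of residual or abnormal tissue or abnormal fluorescence". It makes no distinction by regimen.

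On status, section 1.5 reports: "As of January 2019, this protocol completed Part 1, observational, and began Part 2". On doses given: "Of the 296 subjects infused, 110 subjects were administered 2.5 mg/kg and 186 subjects were administered 5 mg/kg of indocyanine green".

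On the second regimen, section 5.1.2 says: "Alternately, subjects may receive a 25 mg dose of indocyanine green administered by the anesthesiology team during induction". Sections 1.6, 3.1 and 6 (Table 2b) say the same. Section 6.3 puts these patients through the same operative visit, without the infusion-suite visit. The reasons given for 25 mg (sections 1.6 and 3.1) are its resemblance to doses used for imaging vessels, less drug, and fewer expected adverse events.

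On the endpoint, section 3.2 defines sensitivity, specificity and the predictive values for second-window ICG. Section 7.1 defines the same quantities for indocyanine green fluorescence in general, with Bayesian 90% intervals and no split by regimen or part. The interim analysis in section 7.2 names only the two mg/kg cohorts.

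**The concern.** A reader of the final report will take Part 1 as the observational groundwork for what surgeons do in Part 2. For the mg/kg regimens there is such groundwork. For 25 mg at induction there is none, because the regimen does not appear among the subjects treated when Part 1 ended.

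Two things are at stake. First, interpretation: Part 1 findings on dose, timing and feasibility come from larger doses given at an infusion visit before surgery, and nothing in the protocol shows that they describe fluorescence from a flat 25 mg given at induction. Section 1.7.1 names both removal of healthy tissue that glows and false reassurance as risks, so accuracy by regimen matters. Second, estimation: under section 7.1 specimens from both regimens enter one set of figures. The result would be a mixture that describes neither regimen and departs from the test named in section 3.2.

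**Working it through.** **Was any Part 1 subject on 25 mg?**

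- Section 1.5 gives 110 at 2.5 mg/kg and 186 at 5 mg/kg. 110 + 186 = 296, which reproduces the stated number infused. Remainder for any other regimen: 296 − 110 − 186 = 0.
- Cross-check on adverse events, section 1.7.1: "36 events in the 5 mg/kg dose cohort and 19 events in the 2.5 mg/kg dose cohort". From the stated percentages, 5 mg/kg gives 10 + 17 + 6 + 3 = 36 of 186 subjects' worth of events, and 2.5 mg/kg gives 7 + 5 + 2 + 3 + 2 = 19 on 110. 36 + 19 = 55, the stated total, with no third cohort.
- A 25 mg subject could not sit inside a mg/kg cohort: 25 mg equals 2.5 mg/kg only at 25/2.5 = 10 kg and 5 mg/kg only at 25/5 = 5 kg, and subjects are adults.
- Consent ledger: 296 infused + 26 non-evaluable + 4 waiting = 326, against 327 consented. One subject is unexplained, so the most that could have been missed is 1.
- The 296 may include early Part 2 subjects. Every infused Part 1 subject is still among them, so the zero holds for Part 1.

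**How far is 25 mg from what was studied?** The protocol gives no weights; 50 to 100 kg is assumed.

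| Weight | 25 mg in mg/kg | Ratio to 2.5 mg/kg | Ratio to 5 mg/kg |
|---|---|---|---|
| 50 kg | 25/50 = 0.50 | 5 | 10 |
| 100 kg | 25/100 = 0.25 | 10 | 20 |

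The interval from injection to imaging also differs, so these ratios show that the regimens are distinct. They do not predict tumor contrast.

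**What does pooling do?** If w is the share of tumor-positive specimens that come from 25 mg subjects, then

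pooled sensitivity = (1 − w) × second-window sensitivity + w × 25 mg sensitivity.

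The pooled figure moves away from the second-window value by w times the difference between regimens. The same form holds for specificity and the predictive values, with w taken over the matching denominator. The protocol does not say how many subjects will get 25 mg. A ceiling by subjects: if 500 counts infusions, 500 − 296 = 204 remain, and 204/500 = 41%. If the 2.5 mg/kg cohort is first filled to the 185 in section 7.2, 185 − 110 = 75 of these are used, leaving 129/500 = 26%. These are upper limits on the share of subjects. Specimens per subject are not given, so the specimen share is unknown.

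**The case against.** The strongest reply is that nothing here conflicts with the design. Section 3.1 expressly gives Part 2 further work on dose and timing, so a new regimen in Part 2 is broadly foreseen. Resection is at the surgeon's discretion, section 1.7.1 says tissue judged too risky to remove will be left, and section 6.3 lets imaging phases be omitted. No section makes Part 1 a gate for each regimen, sets a go/no-go rule, or reports Part 1 accuracy for any dose. All of that stands. A reader might infer that a protective stage was bypassed for 25 mg; the documents do not support that, because they never give Part 1 that role.

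A reader might also compute a 90% interval for the 25 mg predictive value from zero specimens, 5% to 95% under a uniform prior. That only restates the prior and is not evidence about the trial. The January 2019 count likewise says nothing about specimens collected later.

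Finally, it can be said that 25 mg subjects may not reach the primary analysis at all: section 4.7.1 requires visits 2 and 3, and Table 2b has no Visit 3. But section 6.3, in discussing uncertain diagnoses, says every subject and specimen contributes, and section 7.1 excludes no one. The text therefore does not settle the matter, which strengthens the case for stating it.

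**Conclusion.** The point holds as a limit on evidence and a gap in the analysis plan. Part 1 contains no 25 mg induction subjects (0 of 296; at most 1 if the unexplained consented subject is counted), so its results cannot establish accuracy for that regimen. Specimens at 25 mg arise only under Part 2. As section 7.1 is worded they would be pooled with second-window specimens, although section 3.2 names second-window ICG alone.

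The size of any distortion cannot be given: it depends on the specimen share and on the difference in accuracy between regimens, and the documents report neither. The conclusion rests on the January 2019 dose split being complete and on reading section 7.1 literally. The issue is diagnostic accuracy, not toxicity, since the 25 mg dose is the lower one. It is an inexpensive improvement to the plan.

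**What to change.** In section 7.1:

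1. Restrict the primary sensitivity, specificity, PPV and NPV to specimens from second-window subjects, meaning pre-operative mg/kg dosing, in line with section 3.2.
2. Tabulate specimens by regimen and by part.
3. Report the 25 mg estimates separately with their own Bayesian 90% intervals, and state the prior.
4. State that Part 1 results do not establish accuracy at 25 mg.

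Reconcile sections 3.1, 5.1.2 and 6.3 on how the 25 mg regimen relates to the two parts, and section 4.7.1 with Table 2b on whether these subjects are evaluable. No dose or clinical rule is proposed.

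The cost is some wording, one extra table and imprecise 25 mg figures. As an illustration, 21 tumor-positive of 30 fluorescent specimens would give a PPV interval of 55% to 81% under an assumed uniform prior, from Beta(1 + 21, 1 + 9) = Beta(22, 10). The primary estimates also lose whatever specimens the 25 mg subjects would have added.

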3.2 Primary Study Endpoints

The primary end-point of the study is to determine the test characteristics (i.e., sensitivity, specificity, positive predictive value, negative predictive value) of second window indocyanine green in detection of tumors using intraoperative NIR imaging as compared to the standard of care histopathology report.

3.3 Secondary Study Endpoints

The secondary end-point of the study is to identify based on signal to background noise the optimal timing for surgery following infusion of indocyanine green and dose for optimal safety without toxicity for visualization of indocyanine green during intraoperative imaging in nervous system tumors.

3.4 Additional Study Endpoints

Additional study end-points is to compare standard of care dyes with indocyanine green to determine which dye is more accurate and precise.

4 Study Population and Duration of Participation

4.1 Inclusion Criteria

1. Adult patients 18 years of age and older.
2. Patients presenting with a nervous system tumor presumed to be resectable and at risk for local recurrence on pre-operative assessment.
3. Good operative candidate as determined by the treating physician and multidisciplinary team.
4. Subject capable of giving informed consent.

4.2 Exclusion Criteria

1. Pregnant women as determined by urinary or serum beta hCG within 48 hours of surgery.
2. Subjects with a history of iodide allergies.

CONFIDENTIAL

3. Vulnerable patient populations.
 - a. Patients unable to participate in the consent process.
4. History of uncontrolled hypertension (requiring ER admission or ≥ 3 blood pressure medications)

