1.6 Dose Rationale

In this study, the indocyanine green dose began at 5 mg/kg, aligned with previous nonclinical and clinical experience at the University of Pennsylvania. Given the incidence of HTN in our CNS cohort and seeking optimal signal to background ratio, we decreased to 2.5 mg/kg to assess efficacy and safety. Thus, we intend to evaluate dose ranges but will not exceed 5mg/kg. Alternately, based on neurosurgeon plan, patients may receive a 25 mg bolus of ICG at the time of induction administered intravenously by the anesthesiologist. This 25 mg dose of indocyanine green is similar to dosing for other intraoperative vascular visualization. This can cause less usage of the drug, lower risk of adverse event occurrences.

We make no changes to the route of administration.. The most important difference between what is labeled on the package and this protocol is the dose regimen (up to 5 mg/kg) and the amount of time elapsing before intraoperative imaging begins (up to 72 hours). This protocol began with 24-hour infusions the day before surgery based on previous nonclinical and clinical experience at the University of Pennsylvania. Interested in strength of signal to background ratio over extended or shortened timeframes, we allow for a range of up to 72 hours. The rationale for dosing timing prior to surgical intervention is based on the minimal risks with indocyanine exposure, to accommodate logistical scheduling of surgeries, and to collect data on optimal signal to background ratio in various tumor types.

Indocyanine green has been used in a dose-escalation trial up to a maximum dose of 10 mg/kg [\[22\]](#) and in other trials 3-5 mg/kg [\[13, 17-21\]](#). Indocyanine green has a LD₅₀ after IV administration of 50 to 75 mg/kg [\[22\]](#).

As [name] and other researchers have used an IV injection of indocyanine green to obtain imaging sufficient to describe discrepancies in the structure of abnormal hyper-vascularized tissue [\[47\]](#), it therefore stands to reason that we would be able to accomplish our objective of imaging tumors with indocyanine green using a similar dose.

CONFIDENTIAL

This material is the property of the University of Pennsylvania.

Interim data analysis (see [Section 7.2](#)), specifically the fluorescence signal to background ratio, will determine the optimal timing of indocyanine green infusion, which will guide future infusion in this protocol and future protocols.

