4.4 Duration of Study Participation

Each subject participates in the treatment phase of the trial for approximately 2-4 weeks until surgical resection then is followed for 5 years for survival and recurrence.

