5.8 Receiving, Storage, Dispensing and Return

Penn Investigational Drug Service (HUP and PPMC) or PAH Pharmacy is responsible for all aspects of receiving, storage, dispensing and return of the study intervention.

6 Study Procedures

When the infusion is done pre-operatively (Table 2a), study participation consists of 1) a screening visit, followed by 2) an infusion visit 72 hours prior to surgery, and 3) the operative visit.

Table 2a Pre-Op Infusion Schedule of Evaluations

Study Procedure	Visit 1: Screening	Visit 2: Infusion Visit	Visit 3 Operative Visit	Annual Assessment (Until Year 5)
Informed Consent	X			
Review Inclusion/Exclusion Criteria	X			

CONFIDENTIAL

Study Procedure	Visit 1: Screening	Visit 2: Infusion Visit	Visit 3 Operative Visit	Annual Assessment (Until Year 5)
Demographics/Medical History	X			
Physical Examination	X			
Vital Signs: BP, HR, RR	X	X	X	
Height and Weight	X			
Pregnancy Test	X			
Prior/Concomitant Medications	X			
Iodine/Shellfish Allergy Test	X			
Dispense IP		X		
AE/Unanticipated Problems		X	X	
Annual Medical Record Review: Survival, Recurrence				X

AE = adverse event; BP = blood pressure; HR = heart rate; IP = investigational product; RR = respiratory rate

When the infusion is done intraoperatively (Table 2b), study participation consists of 1) a screening visit, followed by 2) the operative visit in which the anesthesiology team may infuse the NIR drug intra-operatively. This will be a 25mg infusion.

Table 2b Intra-op Infusion Schedule of Evaluations

Study Procedure	Visit 1: Screening	Visit 2: Operative Visit	Annual Assessment (Until Year 5)
Informed Consent	X		
Review Inclusion/Exclusion Criteria	X		
Demographics/Medical History	X		
Physical Examination	X		
Vital Signs: BP, HR, RR	X	X	
Height and Weight	X		
Pregnancy Test	X		
Prior/Concomitant Medications	X		
Iodine/Shellfish Allergy Test	X		
Dispense IP to Anesthesia for injection intra-op		X	
AE/Unanticipated Problems		X	
Annual Medical Record Review: Survival, Recurrence			X

AE = adverse event; BP = blood pressure; HR = heart rate; IP = investigational product; RR = respiratory rate

CONFIDENTIAL

This material is the property of the University of Pennsylvania.

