6.1 Visit 1: Initial Consult (approximately 2 weeks prior to operation)

Patients are given the consent form to examine at their leisure and are encouraged to ask questions and have time to have all questions answered. The PI or member of the study team obtains consent from the patient. He/she will be screened for history of iodine/shellfish allergy by clinical staff.

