6.2 Visit 2 (CTRC, Infusion visit within 72 hours before operation)

For subjects receiving ICG with 72 hours of surgery, they will arrive at the Perelman Center for Advanced Medicine Clinical & Translational Research Center, [name] or the ACC, Farm Journal Building at PAH, [name], or the ACC at PPMC, [name] for their infusions at their respective infusion locations within 72 hours prior to the scheduled surgery to receive their injection of indocyanine green by trained nursing staff. The nursing staff places a peripheral IV and calls the pharmacy for the scheduled infusion of up to 5 mg/kg of indocyanine green diluted in sterile water administered intravenously in the dark, over 40 minutes. The nurse monitors subjects pre infusion, during the 40-minute infusion and for 30 minutes post infusion for any signs of anaphylaxis. For all AEs and prescribed treatment, please see **Section 6.5** and **8.2** Expected Adverse Events and Treatment).

During the study visit, subjects' vital signs are monitored as follows: pre infusion; then at 5 minutes after infusion starts, then at every 15 minutes over the 40-60 minute infusion time frame. During the post infusion 30 minute observation period, vital signs are completed at 10-minute intervals and the subject is monitored for any signs of anaphylaxis. The following vital signs are monitored and recorded during each time point: HR, BP, skin color, and oxygen levels (pulse oximetry) and the subject is observed for any adverse sign or symptoms that could include but is not limited to HTN, mild pain or discomfort at infusion site and signs of anaphylaxis. Symptoms are treated according to prescribed interventions outlined in the ICG Treatment Plan.

The Neurosurgeon may want to compare both indocyanine green with other Standard of Care NIR dyes (ex: 5-ALA) intra-operatively to see which dye localizes more accurately and precisely at the region of interest. This may result in using more than one dye for your surgery.

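### The pregnancy exclusion is timed to surgery, not to the dye: the qualifying hCG test is in neither schedule table, and for infusions more than 48 hours before surgery its window opens only after dosing

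*Combined protocol and SAP*

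**What the plan says.** Section 4.2, item 1, excludes "Pregnant women as determined by urinary or serum beta hCG within 48 hours of surgery". Section 4.6 adds that pregnant women are not to be enrolled.

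The row "Pregnancy Test" appears in both schedule tables of Section 6 (2a for pre-operative infusion, 2b for intra-operative dosing). In each it is marked once, under Visit 1, and not at the infusion or operative visit. The heading of Section 6.1 places Visit 1 about two weeks before the operation, and Section 4.4 describes a treatment phase of "approximately 2-4 weeks until surgical resection".

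Section 5.1.2 has the single dose of up to 5 mg/kg "injected intravenously in the dark, within 72 hours of the operation", and the heading of Section 6.2 reads "Infusion visit within 72 hours before operation". The text introducing Table 2a puts the infusion visit at 72 hours before surgery. Section 1.6 records an earlier practice: "This protocol began with 24-hour infusions the day before surgery". The alternative is 25 mg at induction.

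At the infusion visit, "The nursing staff places a peripheral IV and calls the pharmacy for the scheduled infusion". Section 6.2 calls for vital signs before the infusion but names no pregnancy test and no check of a result. Section 6.3 names none either.

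**The concern.** A pregnancy exclusion in a single-dose imaging study exists to prevent exposure to the dye, so the result that decides eligibility has to be known before the dose. Section 4.2 ties that result to surgery, a different and sometimes much later event.

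There are two separate consequences. The first is scheduling and touches both routes: staff who work from the tables will not do the test that Section 4.2 calls for. The second is ordering and touches one subgroup: when the infusion is given more than 48 hours before surgery, the qualifying test cannot come first, however carefully the protocol is followed.

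What is at stake is the exposure of an undetected pregnancy to up to 5 mg/kg of dye, a dose regimen that Section 1.6 itself names as a main departure from the label. The diagnostic-accuracy analysis is not at stake.

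**Working it through.** No sample-size or error-rate figure is involved. The check compares time windows, all counted back from surgery.

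**Inputs**
- Qualifying hCG test: 48 to 0 hours before surgery (Section 4.2).
- Pre-operative infusion: up to 72 hours before surgery (Sections 5.1.2 and 6.2); 24 hours before surgery in the practice described in Section 1.6.
- Dosing at induction: taken as 0 hours.
- Only scheduled pregnancy test: Visit 1, about 14 days before surgery (Tables 2a and 2b, read with Section 6.1). The tables give no day for Visit 1, so this is approximate.

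**Is the scheduled test the qualifying test?** 14 days × 24 = 336 hours, and 336 − 48 = 288. The scheduled test falls about 288 hours before the Section 4.2 window opens, so it does not meet the criterion.

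**Can the qualifying test precede the dye?** For dye given *t* hours before surgery, the window opens *t* − 48 hours after dosing when *t* exceeds 48. Otherwise 48 − *t* hours are available for the test before dosing.

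| Dye given, hours before surgery | Calculation | Result |
|---|---|---|
| 72 | 72 − 48 | window opens 24 h after the dye |
| 60 | 60 − 48 | window opens 12 h after the dye |
| 48 | 48 − 48 | window opens as the dye is given |
| 24 | 48 − 24 | up to 24 h available before the dye |
| 0 (induction) | 48 − 0 | about 48 h available before the dye |

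**How old is the scheduled test at dosing?**

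| Dosing time | Visit 1 at 14 days | Visit 1 at 28 days (assumption) |
|---|---|---|
| 72 h before surgery | 14 − 3 = 11 days | 28 − 3 = 25 days |
| Day before surgery | 14 − 1 = 13 days | 28 − 1 = 27 days |
| Induction | 14 − 0 = 14 days | 28 − 0 = 28 days |

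The last column assumes that the two to four weeks in Section 4.4 are counted from Visit 1. The document does not say so, and the conclusion does not depend on that column.

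**The case against.** The strongest reply is that the two halves differ in weight. Section 4.2 is itself binding, and a missing mark in a table does not cancel it. For day-before infusion or dosing at induction, a site that follows Section 4.2 can test before the dye, so for those patients the gap is a table correction. That is right. The ordering conflict is confined to infusions more than 48 hours before surgery.

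That subgroup may be small. The protocol started with day-before infusions, and the documents count neither infusions at 48 to 72 hours nor women of childbearing potential. The hours above therefore measure the timing gap, not the risk. But the early infusion is no remote case: the text above Table 2a describes the infusion visit at exactly 72 hours.

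A pregnancy test does precede the dye, at screening, and nothing in the documents shows fetal harm. Section 1.5 reports no maternal or fetal reactions, but in women at full term and without a dose. That says little about an early pregnancy, which is the kind that a test two weeks old would miss. Section 8.6 provides follow-up once a pregnancy is confirmed; it does not prevent exposure.

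The Study Flowchart and case report forms listed in Section 15 were not available and may add a test. They would not change the anchor in Section 4.2.

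**Conclusion.** The concern holds. For women of childbearing potential infused between 48 and 72 hours before surgery, the test that decides the exclusion becomes possible only after the single dose, by up to 24 hours. At other dosing times the criterion can work, but neither table schedules the test it needs, and the one scheduled test is about 11 to 14 days old when the dye is given.

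The remaining exposure is limited to pregnancies that began, or became detectable, after screening. Its frequency cannot be estimated from the documents. The finding rests on the protocol text and tables, and on reading the screening column as the visit described in Section 6.1. It is a participant-protection point that should be corrected; it does not alter the primary endpoint or its analysis.

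**What to change.** Tie item 1 of Section 4.2 to dosing: for example, a negative urine or serum hCG within 48 hours before any study dye, with the exact window set by the clinical team. Mark the test at Visit 2 in Table 2a, before the infusion, and at the operative visit in Table 2b, before induction. State in Sections 6.2 and 6.3 that the result must be known before the dye is given.

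The cost is one amendment: one criterion, two table rows and one sentence in each of two sections. The flowchart and case report forms should be checked for consistency, and dosing staff gain one check. No test is added to the one already required, but there is a trade-off: with a 72-hour infusion the test could fall up to 72 + 48 = 120 hours before surgery. If the surgical team also wants a result close to the operation, that would be a second test. For preventing dye exposure, the test before dosing is the one that matters.
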